Potential clients will receive a medical history screening and a genital examination conducted by the VMMC provider to determine that they are in overall good physical health. Additional inclusion criteria include the following:

- Male aged 13 years and older
- Uncircumcised following physical assessment
- Seeking medical circumcision at one of the evaluation sites

- Consents to an HIV test.
- Agrees to be circumcised using the ShangRing device
 - Those aged 13-17 years will also require parental/guardian approval in order to be included in addition to providing assent. Parents must also agree to be present at the facility during the circumcision (though not in the operating room unless requested by the client), for the discharge instructions, and for subsequent follow-up visits.
- Penis fits into one of the 18 ShangRing ring sizes
- Able to understand the evaluation procedures and requirements
- Agrees to abstain from sexual intercourse and masturbation, for six (6) weeks post removal, seven (7) weeks total
- Lives within 30 kilometers of the facility in Shinyanga, Tanzania
- Willing to provide valid contact information (i.e. telephone number, address of residence, place of employment and other locator information) and willing to receive communications and/or follow-up visits, clients may also be asked for names of relatives or friends to be contacted in the event that the client cannot be reached
- Has an activated cell/mobile phone or access to a cell/mobile phone
- Agrees to return for a follow-up visit to assess healing day 49 post-placement (42 days post-removal).
- If not healed at the day 49 post-placement visit, agrees to return for weekly follow up visits until healed.
- Agrees to a 10 day post-placement (3 days post-removal) telephone call to assess and detect symptoms of AEs
- Able to communicate in English and/or Swahili
- Capable and willing to provide written informed consent (18 years and older), or written informed consent from a parent guardian (13-17 years) to participate for both HTS and VMMC services.

Client Exclusion Criteria

Clients who do not meet the inclusion criteria above and who have the following known medical conditions will be excluded from the evaluation:

- Cognitive impairment that prevents the client from providing consent

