The ShangRing device is intended for single use only and is supplied in a sterile environment. All ShangRing devices removed from clients will be destroyed before disposal. Specifically, the elastic ring is destroyed by cutting it with a scalpel, and the inner ring is destroyed by breaking it with a cutter. Surgical tools used during the ShangRing removal will be sterilized between procedures using an autoclave in accordance with infection prevention and control policies at the clinics.

Key Post-Placement Procedure Counseling following ShangRing Circumcision

Following each circumcision with the ShangRing device, all clients will receive post-circumcision counseling. This counseling will occur on the day that the circumcision is performed and the ShangRing device is placed, and will stress the following messages:

- When to return for the follow-up visit (day 7) for removal of the ShangRing.
- The importance of abstaining from sex or masturbation for 7 weeks (49 days), following the placement of the ShangRing device, or until the penis is fully healed (whichever comes last).
- The importance of good hygienic practices while the device is in place and the wound heals, and how to keep the penis and wound clean and free of potential infection, and strategies to mitigate the risk of tetanus.
- The client will be instructed to return to the evaluation site in case of any unexpected event, for example if there is difficulty urinating, increasing swelling with discoloration of the penis, signs of infection (purulence), severe or increasing pain, the ring spontaneously detaches before day 7, or any other significant concern that they may have.
- The client will also be advised that painful erections may occur during the night.

- All clients will be provided with a phone number for the facility, and encouraged to call any time with any questions or concerns.
- All clients will be provided with a pamphlet with the above information, as well as with contact information for additional counseling if so desired (see Appendix XIII).

Key Post-Device Removal Counseling following ShangRing Circumcision

Following the removal of the ShangRing during the day 7 follow-up visit, all clients will receive additional counseling. This counseling will stress the following messages:

- A phone call to the client to take place in 3 days to assess symptoms of AEs.

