- When to return for the day 49 (42 days post-removal) visit to assess healing. And the importance of returning for that assessment.
- The importance of good hygienic practices while the wound heals, and how to keep the penis and wound clean and free of potential infection, including the importance of tetanus mitigation strategies.
- The client will be instructed to return to the evaluation site in case of any unexpected event, for example if there is severe discoloration of the penis, signs of infection (purulence), severe or increasing pain, or any other significant concern they may have.
- The client will be advised that painful erections may occur during the night.
- All clients will be provided with a phone number for the facility, and encouraged to call any time with any questions or concerns.
- All sexually active clients will be offered a package of condoms to take home.
- The importance of continued abstention from sex or masturbation for 6 weeks (42 days), following the removal of the ShangRing device, or until the penis is fully healed (whichever comes last).

Key Post-Device Removal Counseling during AE Assessment Call

Three days following the removal of the ShangRing, all clients will receive a phone call to assess for symptoms of AEs. If the client is determined to be exhibiting signs of an AE, they will be advised to immediately return to the site that performed the circumcision for treatment. During this call, implementation pilot staff will also remind clients of the following:

- The importance of good hygienic practices while the wound heals, and how to keep the penis and wound clean and free of potential infection, including the importance of tetanus mitigation strategies.
- The client will be reminded to return to the evaluation site in case of any unexpected event, for example if there is severe discoloration of the penis, signs of infection (purulence), severe or increasing pain, or any other significant concern they may have.
- The client will be reminded that painful erections may occur during the night.
- All clients will be reminded that they are encouraged to call any time with any questions or concerns.
- The importance of continued abstention from sex or masturbation for 6 weeks (42 days), following the removal of the ShangRing device, or until the penis is fully healed (whichever comes last).
- When to return for the day 49 (42 days post-removal) visit to assess healing. And the importance of returning for that assessment.

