Wants to be circumcised	Yes 	No 
Is uncircumcised	Yes 	No 
HIV sero-negative	Yes 	No 
Able to communicate in English or Swahili	Yes 	No 
Lives within 30 km of the facility	Yes 	No 
Agrees to be circumcised using the ShangRing device	Yes 	No 
Capable and willing to provide written informed consent (18 years and older), or written informed consent from parent (13-17 years)	Yes 	No 
If 13-17 years old, parent/guardian agrees to be present during circumcision (skip if client is older than 17)	Yes 	No 
Penis fits into one of the 18 ShangRing ring sizes	Yes 	No 
Able to understand the evaluation procedures and requirements	Yes 	No 
Agrees to abstain from sexual intercourse and masturbation, for six (6) weeks post removal (i.e., seven (7) weeks total)	Yes 	No 
Willing to provide valid contact information (i.e., telephone number, address of residence, place of employment and other locator information)	Yes 	No 
Has an activated cell/mobile phone or access to a cell/mobile phone	Yes 	No 
Agrees to complete brief evaluation surveys to assess satisfaction: post-placement and post-removal	Yes 	No 

Any "NO" answer disqualifies the subject from participating in the evaluation

Exclusion Criteria	(check appropriate box)	
Male below 13 years	Yes 	No 
Correct fitting ShangRing size is not available	Yes 	No 
Has the following diseases: hypospadias, hydrocele, scrotal hernia, balanitis, epispadias	Yes 	No 
Known bleeding/coagulation abnormality	Yes 	No 
Is cognitively impaired	Yes 	No 

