Appendix XVII – ShangRing Post-Operative Care Instructions

Post-Operative Instructions

These post op care instructions will be included in pre-and post-procedure counselling for each client. For minors, the same guidance will be given to parents or guardians. A copy will also be given to clients or parents/guardians to carry home.

Wearing the ShangRing

1. It is recommended that, back at home, you rest until you have gotten used to the ShangRing being in place.
2. Do not try to remove or reposition the ShangRing yourself, and keep the penis clean and dry.
3. After the day of circumcision, you may shower or use clean bottled water to rinse the wound while the ShangRing is in place as long as you carefully dry the penis and ShangRing afterwards. Do not go swimming or wash in a bathtub.
4. Do not take part in any intensive activities (e.g. playing soccer or other strenuous manual work in construction sites or farms) to avoid dislocation of the ring. In the case of heavy sweating, be sure to clean and dry the body immediately to keep the wound from being infected, which would delay healing.
5. DO NOT HAVE SEX (INCLUDING MASTURBATION) while the ShangRing is in place. This can damage the wound, displace the device, and increase risk of infection and transmitting diseases.
6. Try not to allow your penis to dangle freely. Tightly fitted briefs are recommended in order to keep the penis from drooping downward and to keep the ring in place and avoid skin abrasion.
7. In the event that you experience mild pain (including during an erection), especially in the first few days after the circumcision, over-the-counter pain medications such as paracetamol (acetaminophen), naproxen or ibuprofen can be used for pain relief. If the pain is excessive, contact your health care provider for further advice. Urinating may help to quickly end an erection.
8. Keep the circumcised area clean and dry. This will promote proper healing. When urinating, use a piece of toilet paper or cloth to prevent urine from seeping into the circumcision area, possibly resulting in infection.
9. Do not apply ointment or cream on or around the circumcised area. Also you should not apply traditional remedies or any other substances (e.g. herbs, soil, cow dung). This may slow the healing process, and can also increase risk for infection, including tetanus, which can be fatal.

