10. You may experience slight swelling around the ShangRing. This is normal as long as it does not cause you too much discomfort. Wearing tightly fitted briefs to keep the penis facing up should help prevent swelling.

Post-operative Care instructions

11. Seven days after your circumcision, return to the clinic to have the ShangRing removed. Do not try to remove or reposition the ShangRing yourself. This can cause serious bleeding or infection. If the device does come off or gets moved, contact the clinic immediately

After Removal of the ShangRing

1. Keep the bandage clean and dry and remove the bandage before going to sleep. In the event that the bandage does get wet, replace the bandage immediately. Replace the bandage in the morning after removal and repeat for one additional day. Starting on the third day, you can wash the penis and the wound area normally and leave the bandage off.
2. Do not apply ointment or cream on or around the wound. Also you should not apply traditional remedies or any other substances (e.g. herbs, soil, cow dung). This may slow the healing process, and can also increase risk for infection, including tetanus, which can be fatal.
3. DO NOT HAVE SEX (INCLUDING MASTURBATION) within the 6 weeks after your circumcision or until the wound has healed completely. Early sex can damage the wound and increase risks of disease transmission. If you absolutely cannot avoid having sex before 6 weeks, masturbation is safest, and sex with condoms is safer than unprotected sex. After six weeks, you should use condoms to protect the circumcision wound (as well as to reduce the transmission of HIV and other infections) for three months, even after it appears completely healed.
4. Expect the complete healing of the wound may take 3 to 4 weeks, or longer.

When to come to clinic or call your doctor

While wearing the ShangRing or after removal, contact your health care provider at cell phone #:

_____ or _____, or visit the clinic:

1. If you notice bleeding from around the ShangRing or from the wound after the ShangRing surgery or the ShangRing removal.
2. If you experience difficulty passing urine.
3. If you experience seriously painful swelling, increasing redness, bruising, elevated temperature around the wound, fever, or the discharge/appearance of pus.
4. If there is severe swelling around the ShangRing, or around the area in which the ShangRing was placed which causes you discomfort.

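### The take-home care sheet ends abstinence six weeks after circumcision (day 42), a week before the day 49 end point used elsewhere, and omits the whichever-comes-last rule

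*Protocol*

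**What the plan says.** **The care sheet (Protocol, Appendix XVII).** Item 3 under the heading on care after removal bars sex and masturbation "within the 6 weeks after your circumcision or until the wound has healed completely". The same item goes on to advise on sex before six weeks, then on condom use after six weeks. Item 4 says healing may take 3 to 4 weeks, or longer. Item 11 fixes the time origin: "Seven days after your circumcision, return to the clinic to have the ShangRing removed". The introduction says the instructions form part of counselling before and after the procedure, and adds: "A copy will also be given to clients or parents/guardians to carry home".

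**The rest of the Protocol.**

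- Client Inclusion Criteria: "Agrees to abstain from sexual intercourse and masturbation, for six (6) weeks post removal, seven (7) weeks total".
- Appendix VII, screening form: "Agrees to abstain from sexual intercourse and masturbation, for six (6) weeks post removal (i.e., seven (7) weeks total".
- Key Post-Placement Procedure Counseling: abstinence "for 7 weeks (49 days), following the placement of the ShangRing device, or until the penis is fully healed (whichever comes last". The same list promises a leaflet: "All clients will be provided with a pamphlet with the above information".
- Key Post-Device Removal Counseling, the AE assessment call on day 10, and the closing reminders in Appendix XXII: abstinence "for 6 weeks (42 days), following the removal of the ShangRing device, or until the penis is fully healed (whichever comes last".
- Male Circumcision Using ShangRing Device: at the removal visit the client is told six weeks or clinical healing, whichever is later. The same paragraph equates six weeks later with day 49.
- Follow-Up Visits: at the day 49 visit the client is told he may resume sexual activity if the wound is judged healed. If it is not, he is told to go on abstaining.

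**The concern.** The client agrees to seven weeks of abstinence as a condition of entry, and then takes home a sheet that says six. The sheet's limit passes a week before the examination that is meant to clear him to resume. Because the sheet is also part of the counselling, staff who follow both texts would give two different end dates aloud.

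The missing later-of rule adds to this. Everywhere else a fixed period is paired with healing, the counselling says the later of the two governs. The sheet joins them with a bare *or* and then turns to condom use after six weeks, which presupposes sex from day 42.

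The sheet itself warns that early sex can damage the wound and raise the risk of disease transmission, and HIV-positive men are enrolled. Healing at day 49 is a secondary endpoint, adverse events are also assessed at that visit, and the healing analysis is meant to inform advice on when sex may resume.

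**Working it through.** This is day arithmetic, with placement (circumcision) as day 0.

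**Inputs**

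- Removal: day 7 (Appendix XVII item 11; Male Circumcision Using ShangRing Device).
- Sheet: 6 weeks from circumcision (Appendix XVII item 3).
- Criterion and screening form: 6 weeks from removal, 7 weeks in total.
- Placement counselling: 49 days from placement.
- Removal counselling, day 10 call and interview reminder: 42 days from removal.

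**Step 1: reproduce the Protocol's own figure.** Removal + 6 weeks = 7 + (6 × 7) = day 49. Counted from placement, 7 × 7 = day 49. The two ways of stating the rule agree with each other and with the 49 days given in the placement counselling.

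**Step 2: the sheet.** 0 + (6 × 7) = day 42. Circumcision cannot be read as removal here, because item 11 puts removal seven days after circumcision.

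**Step 3: the gap.** 49 − 42 = 7 days.

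**Side by side**

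| Place | Fixed end | Later-of rule stated |
|---|---|---|
| Appendix XVII item 3 | day 42 | no |
| Client Inclusion Criteria; Appendix VII | day 49 | no |
| Placement counselling | day 49 | yes |
| Removal counselling; day 10 call; Appendix XXII | day 49 | yes |
| Removal visit text | day 49, by context | yes |
| Day 49 visit | day 49, only if healed | healing required |

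**Step 4: the literal reading of *or*.** If a client takes healing as an alternative end point, item 4 invites him to stop at 3 to 4 weeks. That is days 21 to 28 counted from circumcision, or days 28 to 35 counted from removal (the sheet does not say which). Both fall before day 42.

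**Step 5: does the last week matter?** The Introduction cites a field study with 85.7% of HIV-positive and 87.3% of HIV-negative men healed at 35–42 days. Assume those rates apply here and that the interval ends near day 42; the Protocol does not say where that count starts. The number unhealed would then lie between 575 × (1 − 0.873) = 73 and 575 × (1 − 0.857) = 82. This is only an illustration.

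**The case against.** **The sentence is a prohibition.** Told not to do something during one period or until an event, many readers would take both limits to bind, which is in effect a later-of rule. On that reading an unhealed client is still barred at day 42, and the gap affects only those who appear healed by then. This is a fair reading, and it narrows the problem. It does not remove it: the explicit wording used elsewhere is absent, and the fixed minimum is still a week short.

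**Clients hear the right date repeatedly.** They agree to seven weeks at screening and hear the day 49 rule at placement, at removal and on the day 10 call. The consent and assent pages, which may also state a period, were not available for review. This limits the likely harm. But the sheet is the text the client keeps, and its introduction makes it part of the same counselling.

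**The leaflet promised at placement may be a separate document that does carry the 49-day rule.** The Protocol cites Appendix XIII for it, which is now the phone script. However, neighbouring references are displaced by four: XII points to what is now XVI, XIV to XVIII and XV to XIX. By the same shift XIII becomes XVII, the care sheet. This is strong but inferential evidence, and the conflict with the inclusion criterion does not depend on it.

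**A day 42 label also survives on the follow-up form.** Appendix XII calls the healing visit day 42 post-placement. It sets no abstinence date, so it is not a second source for the sheet's rule, but it would remain out of line if only the sheet were corrected.

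**The figure of 575 counts sheets issued, not clients affected.** This stands. Those affected are clients who resume between day 42 and day 49, and their number is unknown.

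**Conclusion.** The inconsistency is real. The take-home sheet's fixed abstinence period ends on day 42, and every other place in the Protocol that fixes an end point gives day 49, either explicitly or, in the removal-visit text, by context. The shortfall is 7 days, and the sheet also lacks the explicit rule that the later date governs. It reaches all 575 planned clients.

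The conclusion rests only on the Protocol's wording and on removal at day 7. The sample size and the analysis are untouched. No effect on the adverse event or healing results can be calculated from the document. It should be corrected because it is a safety instruction that contradicts the entry criterion and expires before the clinical check it should lead up to.

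**What to change.** Reword Appendix XVII, item 3 after removal, so that abstinence runs *for 6 weeks after removal of the ShangRing (7 weeks after your circumcision) or until the wound has healed completely, whichever comes last*. In the same item, tie the two later mentions of six weeks (the advice on sex before that point and on condoms after it) to the same end point. The earliest end then becomes 7 + 42 = day 49, which matches the rest of the Protocol.

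Two related items can be corrected in the same edit: the day 42 visit label in Appendix XII and the outdated appendix reference for the leaflet in the placement counselling.

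The essential cost is rewording one appendix item before the sheet is printed and notifying the ethics committee. No data collection, sample size or analysis needs to change.

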Appendix XVIII – Adverse Event Reporting Form

Client ID:

Device Related Events Form

Has the participant experienced a device related event per protocol? This includes mild, moderate and severe AE, expected side effects such as common post-operative findings, occurrences resulting from participants' failure to follow instructions, and device malfunctions. Please consult the *Adverse Event Classifications and Definitions: During Device Placement or Wearing and During or After Device Removal* for clarification and definition of adverse events. If the client is determined to have experienced an adverse event, please complete below.

If this is an AE defined as moderate or severe, also fill in the corresponding AE form. Note, that notifiable adverse events must also be reported also per PEPFAR and national guidelines.

Client ID:

Device Events Form

Device Event (Indicate type)	Evaluation Phase	Start/Onset
 Anesthetic Related Problem	During placement  While in place  (before discharge)	Date:
 Bleeding	During removal  After removal 	Time:
 Pain		
 Scarring/Disfigurement Poor cosmetic result or excess skin removal	Severity (Consult definitions for grading classification)	Events/AE Code (Consult definitions for codes)
	Mild 	
	Moderate 	
	Severe 	
 Device Displacement	Moderate or Severe AE	Relationship to Device
 Device detachment	Yes  No 	Unrelated 
 Infection	If "Yes," complete adverse events form	Possibly 
 Injury to penis		Definitely 
 Sexual effects/ undesirable sensory changes		
 Wound Disruption	Action	Pain VAS (see below)
 Excess swelling of penis/scrotum	None  Pharmaceutical 	
 Hematoma	Surgical  Non-surgical 	
 Difficulty with removal	Evaluation termination 	
 Difficulty urinating	Other  Specify: _____	
 Excessive skin removal		
 Other		
	Complete when resolved or at final visit	
	Outcome	End/Termination
	Resolved  Resolved with sequel 	Date:
	Persistent  Unchanged 	Time:
	Unknown 	

Visual Analog Scale (VAS):

I have checked all data introduced to this form until this point and verified that they are complete, correct and reconcilable with the original documentation.

Evaluation Coordinator's Signature: _____

Date: _____

Client ID:

Adverse Events (AE) Form

Has the participant experienced a moderate or severe AE per protocol? If "No", do not enter information on this form. If the AE is defined as severe, notify the principal investigators based on the evaluation protocol.

Adverse Event	Start/Onset	Status	Device Event Number
	Date: Time: Date/time observed (if different):	New  Ongoing 	
	Action	Severity (Consult definitions for grading classification)	AE Code (Consult definitions for codes)
	None  Pharmaceutical  Surgical  Non-surgical  Evaluation termination  Other  Specify: _____	Moderate  Severe  If severe, complete information below	
	Date of SAE report to evaluation investigators:	Was the SAE a result of protocol departure? Yes  No  If "Yes," please specify:	
	Date of last visit and last visit number:	Date the device was applied:	
	Please describe the SAE in block letters (use following page if additional space is needed):	Choose criteria for SAE:  Death  Permanent disability  Life threatening  Hospitalization or prolongation of inpatient hospitalization  Required intervention to prevent one of the above  Other: _____	
	Outcome	End/Termination	
	Resolved  Resolved with sequel  Persistent  Unchanged  Unknown 	Date: Time:	

Please add any additional comments related to this AE. Please write in block letters and sign and date your comments.

I have checked all data introduced to this form until this point and verified that they are complete, correct and reconcilable with the original documentation.

Evaluation Coordinator's Signature: _____ Date: _____

Appendix XIX: Adverse Event Classifications and Definitions: During Device Placement or Wearing and During or After Device Removal*

Adverse Event	Mild	Moderate	Severe
During Device Placement or Wearing			
AN: Anesthetic Related Problem (A1-AN)	Mild localized swelling allergic reaction at injection site without swelling and systemic reaction.	Reaction to anesthetic including light-headedness, nervousness, dizziness that resolves spontaneously and not requiring use of medicines or equipment from the emergency cart/kit/list of emergency commodities at VMMC site and no transfer to another facility or admission to hospital.	Symptoms of severe systemic allergic reaction to local anesthetic including rash, urticaria, angioedema, and shortness of breath, or symptoms of overdose of local anesthetic including light-headedness, nervousness, confusion, dizziness, drowsiness, ringing of ears, blurred or double vision, sensations of heat, cold or numbness, twitching, tremors, convulsions, unconsciousness, respiratory depression, bradycardia, or hypotension requiring use of medicines or equipment from the emergency cart/kit/list of emergency commodities or hospitalization to manage.
BL: Bleeding	A1/A2-BL: Bleeding during placement or wearing that is more significant than usual or spotting of the bandage or clothing with blood; both easily controlled	A1/A2-BL: Bleeding during placement or wearing that requires a pressure dressing to control without surgical re-exploration of the wound or removal of the device.	A1/A2-BL: Bleeding during placement or wearing that requires blood transfusion, transfer to another facility, or hospitalization; or bleeding that requires surgical exploration, removal of device, placement of sutures, hospitalization, or transfer to another facility.
PA: Pain	A1-PA: Client expresses discomfort, however is able to remain still and cooperate for the procedure.	A1-PA: Client expresses discomfort and is not able to cooperate well with procedure.	A1-PA: Client rates pain as very severe.
SD: Scarring/disfigurement/ poor cosmetic result; excess skin removal; injury to penis	Excess skin removal —NA A1-SD: Injury to penis —limited superficial injury not requiring additional intervention.	Excess skin removal —NA A1-SD: Injury to penis —abrasion or small laceration of the glans or shaft	Excess skin removal —NA A1-SD: Injury to penis —injury that requires surgical intervention to stop bleeding or repair.

		requiring pressure dressing, but surgical repair is not required.	
During or After Device Removal			
BL: Bleeding	B/C-BL: Small amount of bleeding from wound with no active bleeding and is controllable with new dressings or 5–10 minutes of manual pressure.	B/C-BL: Bleeding that is not controlled by new dressings or 5–10 minutes of manual pressure or requires a special return to the clinic for a pressure dressing or additional skin sutures without surgical re-exploration of the wound.	B/C-BL: Bleeding that requires surgical re-exploration, hospitalization, or transfer to another facility; or any case where blood transfusion or intravenous fluid is necessary.
DD: Device Displacement	A2-DD: NA	A2-DD: Displacement of the device, including intentional movement of device by the client and/or self-removal that does not require surgical intervention to correct, either because the device can be removed, repositioned, or replaced with a new device.	A2-DD: Displacement of the device, including intentional movement of device by the client and/or self-removal, that requires surgical intervention to correct, or requires hospitalization or transfer to another facility to clinically manage.
IN: Infection	B/C-IN: Erythema or traces of serous discharge or infective process noted at wound margin. No intervention other than improved wound hygiene.	B/C-IN: Discharge from the wound, painful swelling with erythema, or elevated temperature that requires use of oral antibiotics.	B/C-IN: Cellulitis or abscess of the wound, or infection severe enough to require surgical intervention, hospitalization, or intravenous or intramuscular antibiotics.
PA: Pain	A2/B/C-PA: Client complaints of pain, not requiring more than standard postoperative analgesics and considered within normal thresholds associated with surgery	A2/B/C-PA: Pain serious enough to result in disability (as evidenced by inability to work or perform activities of daily living) lasting for at least 1 day after device placement or removal. For programmes that utilize a visual analogue scale (VAS) for rating severity, a VAS score of 5–7 (on a 1–10 scale).	A2/B/C-PA: Pain serious enough to result in disability (as evidenced by inability to work or perform activities of daily living) lasting 2 or more days after device placement or removal. For programmes that utilize a visual analogue scale (VAS) for rating severity of pain, a VAS score of 8–10 (on a 1–10 scale).
SD: Scarring/disfigurement/ Poor cosmetic result; excess skin removal (C-SD)	Scarring -complaints by client in the absence of discernible abnormal scarring/disfigurement. Torsion of	Scarring -Discernible but re-operation not required. Usually noticed first by the client and reported to the	Scarring -Discernible and requires reoperation or referral/transfer to another facility.

	
penis—torsion present but does not cause pain or discomfort.
 
Insufficient skin removal—prepuce extends over the coronal margin but less than one third of the glans is covered in flaccid state.
	
provider. Torsion of penis—torsion present that causes mild pain or discomfort with erection but does not require surgery to correct.
 
Insufficient skin removal—prepuce partially covers glans when flaccid but surgical correction is not necessary.
	
Torsion of penis—torsion present. Erections are painful and client cannot tolerate the appearance, discomfort, or pain. Surgery needed for correction.
 
Insufficient skin removal—prepuce covers most of the glans when flaccid and surgical correction is necessary.

Injury to Penis	A2/B/C-SD: Injury to penis —limited superficial injury not requiring additional intervention.	A1-SD: Injury to penis —bruise or abrasion of the glans or shaft requiring pressure dressing, but surgical repair is not required.	A1-SD: Injury to penis —injury that requires surgical intervention to stop bleeding or to repair. Severing of the glans or shaft, injury to urethra or development of a fistula is also considered a severe AE.
Excess Skin Removal	C-SD: Excess skin removal —slight tightening of the skin observed; no surgical correction needed.	C-SD: Excess skin removal —pulling of scrotal skin onto the penile shaft and wound disruption.	C-SD: Excess skin removal —wound appearance is such that the wound has gaping edges or large or deep defects such that without revision, there would be significant scar formation.
SX: Sexual Effects/Undesirable Sensory Changes	C-SX: Occasional inability to have erection or dissatisfaction with sexual performance, no psycho-behavioral consequences.	C-SX: Post-operative changes that consistently impair or preclude sexual function for 3 to 6 months after surgery not present prior to surgery.	C-SX: Post-operative changes that consistently impair or preclude sexual function for greater than 6 months after surgery that were not present prior to surgery.
WD: Wound Disruption	C-WD: Wound disruption but not extensive enough to require suturing for wound closure.	C-WD: Muco-cutaneous gap > 1.0 cm in width, but no exposure of deeper tissue	C-WD: Wound disruption exposing tissue deeper than subcutaneous tissue or requiring surgical intervention such as suturing or debridement.
OA: Other AEs, Excess swelling of penis/scrotum including hematoma; other	Excess swelling —mild swelling without signs of on-going bleeding.	
Excess swelling—symptoms/signs that require clinical intervention, but not surgical exploration.
 
Other—other adverse events related to surgery that result in disability (as evidenced by loss of work or cancellation of normal activities) lasting for at least 4 days after surgery but not more than 7 days.
	
Excess swelling—surgical exploration required to control bleeding or remove haematoma or symptoms/signs so extraordinary as to cause disability (as evidenced by loss of work or cancellation of normal activities) lasting for at least 8 days after surgery or device placement or removal as pertinent.

			Other —other AE(s) related to the surgery that result in disability (as evidenced by loss of work or cancellation of normal activities) lasting for at least 8 days after surgery or device placement or removal, or result in hospitalization or referral/transfer to another facility.
Difficulty Urinating	N/A	A2/C-OA: Symptoms that resolve with removal/repositioning of the device or dressing (transient difficulty urinating that resolves on its own would not be considered an AE).	A1/C-OA: Complete obstruction and/or requires placement of a catheter, referral for treatment or surgery to correct.

*Adapted from Appendix 3 of *Adverse Event Action Guide For Voluntary Medical Male Circumcision (VMMC) by Surgery or Device, 2nd Edition, 2016*

